## 8. Flow-up

		1 day	1 week (±1 day)	2 weeks (±1 day)	4 weeks (±3 days)	8 weeks (±3 days)	12 weeks (±7 days)	>24 weeks
Subjective perception	Comfort	√						
	Bleeding	√						
	Epiphora, mucopurulent discharge	√	√	√	√	√	√	√
Specimen collection	conjunctival sac		√	√	√	√		
	nasal cavity				√			
Endoscope						√	√	√

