## 9. Expected Risks and Measures to Address Them

1) En-DCR is an invasive procedure and there is a risk of blood leakage from the lacrimal sac-nasal anastomosis in the early postoperative period.

Most of the distant cases fail due to mucosal epithelial tissue hyperplasia, scarring and obstruction of the anastomosis. HBCS can stop diffuse bleeding, inhibit bacteria, and promote wound healing, etc. 5-FU can effectively inhibit the proliferation of fibroblasts. However, the effect of the two as dressings at the anastomosis of the lacrimal sac and nasal mucosa applied to En-DCR is uncertain. We will take appropriate measures if the following situations occur.

- a. Localized infection: intensive anti-infection treatment.
- b. Severe postoperative bleeding: Use other drugs and dressings to stop bleeding.
- c. Granulation tissue, scar proliferation and anastomotic adhesion: excise or separate them, and apply antiproliferative drugs to the wound.
- d. Delayed healing: use other dressings and medications.

2) Adequate and repeated education, obtaining informed consent, establishing timely and effective communication with patients, and standardized follow-up.

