## **10. Statistical methods**

To compare the differences between the adjuvant therapeutic effects of different En-DCR in the three groups: data were analyzed using SPSS 19.0 software, one-way ANOVA was used for age comparison, and Kruskal-Wallis H-test was used for comparison of postoperative comfort and blood leakage. Comparison of gender, complications, and cure rate

was performed by chi-square test, and the difference was considered statistically significant at  $P<0.05$ . Effective rate was compared by Fisher's exact probability method, and  $P<0.05$  was regarded as statistically significant difference, and  $P<0.0167$  was regarded as statistically significant difference for two-by-two comparison. The collected conjunctival sac and nasal flora were analyzed: alpha diversity analysis, PCA analysis, taxonomic composition analysis, and Lefse analysis were used, and differences were considered statistically significant at  $P<0.05$ . Comparisons between groups were made using chi-square test or fisher's exact probability method for adverse events and serious adverse events when necessary.

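### Bleeding is asked about on day 1 only and no visit has a complication or adverse-event item, so later bleeding and early events compared in section 10 may be under-recorded, possibly unevenly

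*Combined protocol and SAP*

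**What the plan says.** **Collection (section 8).** There are seven visits: 1 day, 1, 2, 4, 8 and 12 weeks, and beyond 24 weeks. Under "Subjective perception" the schedule lists comfort and bleeding, each ticked on day 1 only, and "Epiphora, mucopurulent discharge", ticked at all seven visits. The other rows are specimen collection and endoscopy, the latter at 8, 12 and more than 24 weeks. No row is labelled for complications, adverse events or serious adverse events.

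**Expected events (section 9).** The plan says that "there is a risk of blood leakage from the lacrimal sac-nasal anastomosis in the early postoperative period" and calls the effect of the two dressings at the anastomosis uncertain. It then names four problems: localized infection; "Severe postoperative bleeding: Use other drugs and dressings to stop bleeding"; "Granulation tissue, scar proliferation and anastomotic adhesion"; and "Delayed healing: use other dressings and medications". Each has a response. None has a rule for when it is looked for or how it is recorded.

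**Analysis (section 10).** "Kruskal-Wallis H-test was used for comparison of postoperative comfort and blood leakage", with no time point given. Complications are compared by chi-square at P<0.05, with no definition or window. The last sentence provides chi-square or Fisher's exact tests for "adverse events and serious adverse events when necessary".

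**The concern.** Section 10 compares safety outcomes that section 8 collects only in part. The same patients return at 1, 2 and 4 weeks, but nobody is scheduled to ask them about bleeding then. Before 8 weeks nothing scheduled covers healing. In those gaps an event enters the data only if the patient volunteers it or it comes to treatment.

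Two things are at stake. If all groups under-record equally, a real excess in one group becomes harder to see. If they under-record unequally, the comparison can be biased in either direction. Unequal recording is possible because the documents describe no masking, and whether an unsolicited event is written down may depend on knowing the treatment. This matters most for group B, which receives injected 5-FU in a setting where the plan itself calls the effect uncertain.

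**Working it through.** **Step 1. The plan's own figures.** Section 5: 3 × 40 = 120, as stated. Section 10: 0.05 / 3 = 0.0167, as stated. The plan gives no rate for bleeding or complications, so there is no power figure to reproduce.

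**Step 2. Scheduled visits per item, counted from section 8.**

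| Item | Visits | When |
|---|---|---|
| Bleeding | 1 of 7 | day 1 |
| Epiphora and discharge | 7 of 7 | every visit |
| Endoscopy | 3 of 7 | 8, 12, >24 weeks |
| Complications, AEs or SAEs | 0 of 7 | none |

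**Step 3. Section 9 items set against section 8.**

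- Infection: partly covered by the discharge question at every visit.
- Severe bleeding: covered on day 1, not asked about afterwards.
- Granulation, scar, adhesion: visible at endoscopy from 8 weeks, but no list of findings to record.
- Delayed healing: nothing scheduled before 8 weeks.

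**Step 4. Size if late bleeding were asked about.** All rates are assumed. The test is the three-group chi-square with 40 per group. With counts x in each group, total T and e = T/3,

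X² = Σ(x − e)² / [e(1 − T/120)], significant if above 5.99 (2 degrees of freedom, 5% level).

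The power is the binomial probability of all count combinations that reach significance. Groups A and control are held at 5% (40 × 0.05 = 2 patients each).

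| Group B rate | Expected in B | Power |
|---|---|---|
| 10% | 4 | 12% |
| 15% | 6 | 34% |
| 20% | 8 | 60% |
| 25% | 10 | 80% |

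Under the present schedule none of these events is solicited. The counts are small (at 5/20/5%, 2 + 8 + 2 = 12 events, or 4 per group under no difference), so the chi-square power is approximate.

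**Step 5. Effect of uneven recording when the true rates are equal.** Recorded rate = true rate × share captured. For example, at a true rate of 20%, 90% capture gives 40 × 0.20 × 0.90 = 7.2 recorded events in B, and 60% capture gives 40 × 0.20 × 0.60 = 4.8 in each other group. False-positive rate of the same test:

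| Capture, B v others | True 10% | True 20% | True 30% |
|---|---|---|---|
| Complete | 4.5% | 4.9% | 5.0% |
| 70% v 60% | 4.2% | 5.2% | 6.0% |
| 90% v 60% | 6.6% | 10.7% | 15.7% |

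**Step 6. Effect on a real difference.** With true rates of 10% in A and control and 30% in B, power is 67% with complete capture, 34% if half of all events are captured in every group, and 21% if capture is 60% in B and 90% elsewhere. Equal under-recording alone therefore costs about half the power in this example.

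**The case against.** The best defence is that the leakage comparison is coherent as planned. Section 10 pairs comfort with leakage, section 8 collects exactly those two items together on day 1, and section 9 places leakage early after surgery. That stands. A reader might infer that leakage is tested without data, and the documents do not support that. What remains is that the time point is not stated and later bleeding is not asked about.

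Three further limits also stand.

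- **Complications are not wholly uncollected.** Discharge is asked at every visit, and endoscopy can show granulation, scar and adhesion. Section 9 links these to later failures, when endoscopy is scheduled.
- **Missed or uneven events are not shown.** One schedule applies to all groups, and section 9 promises standardized follow-up and a response to severe bleeding. Uneven recording is a risk inferred from unsolicited reporting without described masking.
- **The closing qualifier in section 10 is ambiguous.** A reader might take it as leave to decide, after seeing the data, whether to compare adverse events at all. It can equally mean that Fisher's exact test is used where counts require it. The text does not settle this, so selective analysis should not be alleged.

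The figures also depend on the inputs. Nothing in the documents supports a 30-point gap in capture, or a gap in group B's favour or against it. With a 10-point gap the false-positive rate is close to nominal.

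None of this fills the gap between day 1 and 8 weeks. Treating a severe bleed is not the same as recording bleeding systematically, and milder bleeding has no scheduled route into the data after day 1.

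**Conclusion.** The point holds in a limited form. Followed as written, the plan solicits bleeding once, solicits complications and adverse events under that name at no visit, and still compares them between groups. Bleeding after day 1 and other early events may be under-recorded, and possibly unevenly.

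The size cannot be fixed from the documents. It rests on assumed event rates and capture shares, a three-group chi-square at 5% and 40 patients per group with complete follow-up. Over the ranges shown, the consequence of uneven recording goes from negligible to about three times the nominal false-positive rate (15.7% against 5%). Asking about late bleeding would give useful power only for a large excess; at 10% against 5% it would detect little. The case for the change does not rest on any single figure: it is cheap, and an answer not asked for at a visit is hard to recover later.

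**What to change.** 1. **Bleeding.** Keep the day-1 leakage comparison and label it as day 1 in section 10. Tick bleeding at the existing 1-, 2- and 4-week visits as well, and compare bleeding after day 1 as a separate result. Do not merge the two into one worst grade, because day-1 bleeding could set the grade in many patients and hide later differences.
2. **Complications and adverse events.** Add one row to section 8, asked in the same words at every existing visit in all groups, built on section 9 items a to d and covering adverse and serious adverse events. At the endoscopies already scheduled, record granulation, scar, adhesion and healing on a fixed list. Before 8 weeks record symptoms only, since a question cannot replace an endoscopic finding.
3. **Analysis.** Reword the last sentence of section 10 so that all adverse and serious adverse events are tabulated by group, with Fisher's exact test where counts are small.

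The cost is three extra ticks, one schedule row, a short endoscopy list and a few words in section 10. Visit forms become slightly longer and more mild events will be recorded. No visit or examination is added, and patient care does not change.
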